### **9.3.8 Inhibitor measurement**

Data documented by the physician, if collected, include:

- Date of measurement.
- Inhibitor test result (negative/positive).
- Titer of inhibitor (Bethesda units).

### **9.3.9 Exploratory Assessment (PEG measurement)**

Data on PEG measurements will be recorded if it is part of the routine practice.

#### **9.3.10 Patient-reported outcomes**

The questionnaires (Hemo-SAT A, Hemo-QoL [A and SF] and WPAI [+ CIQ: HS]) and patient infusion diary will be completed by the patient/legal representative, where applicable.

Patients/legal representatives will be requested to complete the questionnaires during their routinely scheduled visits at the study site.

#### **9.3.11 End of observation**

If available, the date and the primary reason for end of observation/study discontinuation should be stated.

## 9.4 Data sources

The physician collects historical study-relevant data (demographic and clinical characteristics) from medical records, if available, or else by interviewing the patient. Likewise, the physician collects treatment-related data during visits that take place in routine practice.

Each patient is identified by a unique central patient identification code, which is only used for study purposes. For the duration of the study and afterwards, only the patient's treating physician or authorized site personnel are able to identify the patient based on the patient identification code.

In case a patient is seen by more than 1 physician (e.g., the patient is monitored by a physician other than the initial treating physician), the initial treating physician should make every effort to collect information on any visits (including results) that have taken place outside the treating physician's site for example by communicating with the other physician or by having the patient/legal representative obtain a letter with detailed information and results, for example of any ARs, medications given, or procedures performed.

The HJHS is used as source for joint health status. The HEAD-US score is used as source for joint health status of patients with hemophilic arthropathy.

Validated patient questionnaires (Hemo-SAT A, Hemo-QoL [A and SF] and WPAI [+ CIQ: HS]) are used as sources for the patient assessment on satisfaction and treatment adherence. Patients/legal representatives will be requested to complete the questionnaires during their routinely scheduled visits at the study site.

### **Hemophilia Treatment Satisfaction Questionnaire (Hemo-SAT)**

This is a hemophilia-specific treatment satisfaction questionnaire. The Hemo-SAT questionnaire version for adults (Hemo-SAT A) consists of 34 items pertaining to 6 dimensions (Ease & Convenience, Efficacy, Burden, Specialist/Nurses, Center/Hospital, General Satisfaction). The Hemo-SAT A questionnaire is suitable for adult patients and adolescents (>12 years of age) and should be completed at the initial (baseline) visit, at Month 12, Month 24 and Month 36.

### **Hemophilia Quality of Life Measure for Adults (Hemo-QoL-A) and Hemo-QoL Short Form (Hemo-QoL-SF) for Children and Adolescents**

The questionnaire is used to capture the full impact of damoctocog alfa pegol and the treatment modalities on the patients' hemophilia-specific quality of life. Hemo-QoL-A is a hemophilia-specific quality of life questionnaire for adults aged 18 years and above. The questionnaire has 41 items covering 6 domains: Physical Functioning, Role Functioning, Worry, Consequences of Bleeding, Emotional Impact, and Treatment Concerns. For patients younger than 18 years, the Hemo-QoL-SF Questionnaire for children and adolescents (12 to 17 years) is used. The Hemo-QoL-SF contains 35 questions covering 9 domains: Physical Health, View of Yourself, Family, Friends, Others, Sports, Dealing, and Treatment. The respondent burden for both questionnaires is approximately 15 minutes. Patients should complete the Hemo-QoL (A or SF) questionnaire at the initial (baseline) visit, at Month 12, Month 24 and Month 36.

## **Work Productivity and Activity Impairment Scale (WPAI)**

The study will include the Work Productivity and Activity Impairment: Hemophilia Specific (HS) questionnaire also containing classroom impairment questions (CIQ) (WPAI [+ CIQ: HS]).

The WPAI questionnaire has been widely used in PRO work since its initial development over 20 years ago. There have been approximately 40 validation studies regarding the use of this tool in various chronic disease states, as well as for general health. In addition to the validation studies, there are documented uses of the tool in various chronic conditions including hemophilia. A hemophilia specific questionnaire is also available and translated in many languages. It has been recently used in several studies [29].

The WPAI [+ CIQ: HS] assesses the effect of hemophilia on ability to work, attend classes, and perform regular daily activities in ages 12 and above. The questionnaire is self-administered and comprises nine questions that elicit information on work, classroom, and daily activity impairment during the previous seven days. Scores are expressed as percentages of impairment/ productivity loss, with higher scores indicating greater impairment. The respondent burden for this questionnaire is approximately 10 minutes. The assessment should be performed at the initial (baseline) visit, at Month 12, Month 24 and Month 36.

### **9.5 Study size**

The study aims to enroll at least 200 patients. Assuming a dropout rate of 10%, 180 patients will be available for the effectiveness analysis. Based on this sample size, the primary endpoint (total ABR in moderate and severe patients who receive prophylactic damoctocog alfa pegol treatment) can be estimated with reasonably good precision.

It is a standard to assume that ABR follows a negative binomial distribution  $NB(\mu, \theta)$ , where  $\mu$  is the mean ABR of prophylaxis regimen, and  $\theta$  is the dispersion parameter for variance. Previously, the PROTECT study [9] showed an ABR on prophylaxis of 4, with 95% confidence interval (CI) of 3 to 5 per person, and a dispersion parameter of 1. A simulation study shows, if it is conservatively assumed  $\mu=6, \theta=1$ , the half width of 95% CI for mean ABR in the prophylactic population (assuming  $n=180$ ) is no larger than 0.96 with a probability of 0.9. For the subsequent subgroup analysis, precision of mean-ABR estimates depends on the size of each subgroup. Estimated 95% CIs in various scenarios are summarized in Table 4.

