### **9.1.1 Primary endpoint**

The primary endpoint is:

- Mean/median annualized number of reported total bleeds in patients with hemophilia A,

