#### **9.2.6 Representativeness**

The eligibility criteria have been selected to allow for a broad representation of patients within the study. The study will enroll previously treated hemophilia A patients initiating or currently receiving damoctocog alfa pegol with any kind of treatment modality (on-demand, prophylaxis, or intermittent prophylaxis). Prophylaxis therapy is the recommended standard of care for patients with severe disease and those with moderate disease with severe patient bleeding profile. By enrolling eligible patients with mild, moderate, or severe disease, the study will be representative of real-world.

Previously untreated hemophilia A patients are not eligible for this study as the safety of damoctocog alfa pegol in this patient population has not been established. Given the incidence rate of hemophilia A, 1 in 5,000 live male inhabitants, previously untreated patients represent approximately 2% of the hemophilia patient population. Thus, the study population is broadly representative of mild, moderate, and severe hemophilia A patients, even when previously untreated patients are excluded.

In addition, the inclusion of a representative sample of study sites (i.e., health care providers, hospitals, etc.) in terms of geography, practice size, and academic or private practice type is aimed as a measure to enhance the generalizability of study results.

The patients documented in the study should be selected based only on eligibility according to a minimal set of selection criteria (see Sections 9.2.2 and 9.2.3). No further selection should be applied, thus increasing the generalizability of the study results. Physicians will be asked to sample consecutive patients whenever possible. This consecutive sampling approach is intended to reduce selection bias by the treating physicians as to whom to enroll in the study, especially with regard to factors that may be associated to the outcome or prognosis of those patients (e.g., demographic characteristics, multiple co-morbidities, as well as concomitant medications), thus maintaining the observational character and enhancing the external validity of the study. Furthermore, an anonymous patient log file (integrated in the Electronic Data Capture [EDC] system) will be used by each site to document also patients not enrolled in the study (without recording patient-specific data), including the reason for not enrolling (e.g., refused consent, eligibility criteria not met, etc.).

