#### **ABR:**

Summary statistics of the number, type, location, and severity of reported bleeds (total, spontaneous, joint, and trauma) will be presented.

The primary analysis on ABR will be performed in patients receiving prophylactic treatment. ABRs will first be characterized using descriptive statistics by calculating mean ( $\pm$  standard deviation [SD]), median, minimum, and maximum. Further, the mean ABRs along with 95% CIs will be estimated using a negative binomial regression model corrected for over-dispersion, and with relevant treatment and disease characteristics as covariates and observed prophylactic treatment period as an offset variable.

When enough data is collected, additional analyses include: 1) comparing the ABR in patients receiving prophylactic treatment with those who are not treated with standard prophylaxis; 2) comparing the ABR in patients receiving damoctocog alfa pegol prophylactic treatment with the ABR prior to the damoctocog alfa pegol treatment.

Further details of the analysis will be described in the SAP.

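### Section 9.5's precision claim gives an expected confidence-interval half-width (0.96 at n = 180) as one met with probability 0.9, and takes n from dropout alone although the population it names is narrower than enrolment

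*Protocol*

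**What the plan says.** Protocol section 9.5 builds the effectiveness sample size in three steps.

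- Enrolment and retention: "The study aims to enroll at least 200 patients", then "Assuming a dropout rate of 10%, 180 patients will be available for the effectiveness analysis".
- Target quantity: the primary endpoint is described there as "total ABR in moderate and severe patients who receive prophylactic damoctocog alfa pegol treatment".
- Precision: "It is a standard to assume that ABR follows a negative binomial distribution". With mean 6 and dispersion 1, and n taken as 180 in the prophylactic population, a simulation is reported to show that the 95% CI half-width "is no larger than 0.96 with a probability of 0.9".

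Table 4 lists intervals for n = 36, 108 and 180 with half-widths 2.17, 1.23 and 0.96. It does not say whether these are expected values or upper bounds.

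Other sections bear on the n. The inclusion criteria (9.2.2.1) admit on-demand, prophylaxis and intermittent-prophylaxis patients. Section 9.2.6 says "By enrolling eligible patients with mild, moderate, or severe disease, the study will be representative of real-world". Section 9.7.4 says "The primary analysis on ABR will be performed in patients receiving prophylactic treatment", with no limit on severity.

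**The concern.** The 0.96 appears twice in section 9.5: as the half-width of the n = 180 interval in Table 4, and as a value not exceeded with probability 0.9. An interval that illustrates a typical study and a 90% bound should not coincide, because the estimated variance of negative binomial counts varies a good deal between samples.

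The 180 allows for dropout only. Patients with mild disease or on-demand treatment may enrol, but they fall outside the population section 9.5 names, and nothing is deducted for them.

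No hypothesis is tested, so this precision statement carries the whole effectiveness argument for study size. A reader would take from it a 90% assurance about the width of the primary interval.

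**Working it through.** **Inputs, all from section 9.5:** mean μ = 6; dispersion θ = 1; n = 200 × 0.9 = 180; two-sided 95% CI. With θ = 1 both usual negative binomial parameterisations give the same variance. The follow-up per patient used in the protocol's simulation is not stated. One patient-year is taken first, and two and three years are shown as a range.

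**Step 1: reproduce Table 4.** For one patient-year the variance is 6 + 6² = 42.

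- Natural-scale half-width: 1.96 × √(42/n). At n = 180 this is 1.96 × √0.2333 = 0.947.
- Log-scale half-width: 6 × sinh(1.96 × √((1/6 + 1)/n)). At n = 180 this is 6 × sinh(0.1578) = 0.951.

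The last two columns below are simulated, using a negative binomial maximum-likelihood fit with a log-scale interval.

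| n | Table 4 | Natural scale | Log scale | Simulated mean | Simulated 90th percentile |
|---|---|---|---|---|---|
| 36 | 2.17 | 2.12 | 2.16 | 2.12 | 2.71 |
| 108 | 1.23 | 1.22 | 1.23 | 1.22 | 1.42 |
| 180 | 0.96 | 0.947 | 0.951 | 0.946 | 1.06 |

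Table 4 matches expected half-widths at one patient-year to within about 2%. It does not match 90% bounds. With three years each the per-patient variance of the rate is 6/3 + 36 = 38, and the log-scale half-widths become 2.05, 1.17 and 0.90, a poorer match to all three rows.

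The ratio of the rows agrees. Table 4 gives 2.17/0.96 = 2.26. Expected half-widths give 2.12/0.946 = 2.24, while 90% bounds would give 2.71/1.06 = 2.56.

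**Step 2: test the probability.** Simulation of negative binomial data at n = 180, with six ways of forming the interval (Wald, t, negative binomial log scale, negative binomial identity scale, log scale with known dispersion, quasi-Poisson):

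| Follow-up for every patient | P(half-width ≤ 0.96) | Half-width met with probability 0.9 |
|---|---|---|
| 1 year | 0.57–0.60 | 1.04–1.08 |
| 2 years | 0.70–0.74 | 1.00–1.04 |
| 3 years | 0.74–0.80 | about 1.01–1.02 (known dispersion: 0.99) |

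Allowing for rounding (≤ 0.965) raises the one-year figure to at most 0.62. None of these reaches 0.9.

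**Step 3: what would give 0.9.** At one year each, about 216 to 220 analysable patients. Alternatively, n = 200 with three full years from every patient gives 0.90 to 0.92, but that is neither the stated n nor compatible with 10% dropout.

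**Step 4: the population behind n.** The protocol gives no expected share of mild or non-prophylaxis patients, so the shares below are assumptions. They apply to the 180, with one patient-year each.

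| Share outside the section 9.5 population | n | Expected half-width | P(≤ 0.96), log scale |
|---|---|---|---|
| 0% | 180 | 0.95 | 0.57–0.58 |
| 20% | 144 | 1.06 | 0.19 |
| 40% | 108 | 1.23 | 0.03 |

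**The case against.** Five points can be made for the protocol.

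- *Follow-up is longer than one year.* Planned observation is 36 months and the primary model uses observed prophylaxis time as an offset. This stands as a limit on the size of the error. A reader might infer that the true probability is simply 0.57, but that holds only for one patient-year, which the document never states. Three full years still gives only 0.74 to 0.80.
- *180 may be too low as well as too high.* The full analysis set keeps patients without three complete years, and 200 is a minimum. This stands: 180 cannot be called wrong in one direction only, and any shortfall is unknown.
- *The n is conditional.* Section 9.5 takes n = 180 as an assumption for the prophylactic population, and Table 4 already shows smaller n. This stands in part. The same section also ties the primary endpoint's precision to the 180 retained patients, with no deduction for those outside that population.
- *Mean 6 is conservative.* The cited earlier study had an ABR of 4. At mean 4 the variance is 4 + 16 = 20 and the expected half-width at n = 180 is 1.96 × √(20/180) = 0.65. Simulated with a Wald interval at one year, 0.96 is then met with probability above 0.99 at n = 180, 0.99 at n = 144 and about 0.86 at n = 108. This supports the study size, but not a statement made explicitly for mean 6.
- *No decision hangs on it.* There is no test and no precision threshold; the section claims only reasonably good precision. This stands and lowers the severity.

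A reader might also count section 9.1.1, "Mean/median annualized number of reported total bleeds in patients with hemophilia A", as a third primary population. The documents do not support that firmly. The line names the endpoint variable and breaks off at a comma, and the primary objective in 8.1 concerns prophylaxis. The clear difference is between 9.5 and 9.7.4.

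**Conclusion.** The point holds, at moderate severity. The 0.9 attached to 0.96 is wrong for the stated inputs under every interval method and follow-up tried at n = 180. Table 4's widths are sound if read as expected values at one patient-year. At the 90% level the understatement is about 0.05 to 0.12 bleeds per year on a mean of 6, depending on follow-up and method.

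The n = 180 rests on dropout alone, while section 9.5 applies it to a population narrower than the one enrolled. The effect cannot be sized from the protocol; the 20% and 40% shares only illustrate it. Sections 9.5 and 9.7.4 also disagree on whether mild patients on prophylaxis belong to the primary analysis.

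It would be tempting to conclude that the study is too small. The documents do not support that: no precision target is set, the assumed mean is deliberately high, and the purpose is descriptive. What fails is the stated assurance, not the study's ability to estimate ABR.

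**What to change.** In section 9.5:

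1. State the follow-up per patient assumed in the simulation.
2. Replace the probability sentence. For example: assuming one patient-year per patient, the expected half-width at n = 180 is about 0.95, and it is at most about 1.06 with probability 0.9. If another follow-up is intended, recompute both figures for it.
3. Label Table 4 as expected half-widths.
4. Say that 180 is an upper scenario if some enrollees are mild or not on prophylaxis, and give the precision over a range of n, for example 144 (about 1.06) and 108 (about 1.23), naming the shares as assumptions.

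Use one primary population in sections 9.5 and 9.7.4, either with or without the restriction to moderate and severe disease, and report the other as a named secondary summary.

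The cost is a text change and one rerun of a short simulation. The stated precision becomes slightly less favourable. Enrolment, data collection and the analysis model stay as they are; the choice of population only settles which patients enter the primary summary.

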**Table 4: Estimated 95% confidence intervals in various scenarios**

Number of patient	95% CI	Precision based on half width of the 95% CI
36	(4.32, 8.66)	± 2.17
108	(4.92, 7.39)	± 1.23
180	(5.16, 7.07)	± 0.96

Sample size justification is further based on the need to observe a rare AE, and it is reasonable to assume that the number of patients in the safety analysis set (SAF) is close to the target enrollment (i.e., at least 200).

Table 5 presents the expected probabilities of observing a specific number of patients with events in the study under varying underlying incidence risks. The table indicates that 200 patients will provide an adequate chance of observing events with event rate larger than 2.0%, as there is a 76.5% chance of observing at least 3.

**Table 5: Probability of observing patients with events with increasing sample size**

Number of patients	Observed patients with events (x)	Probability(%) of observing at least x patients			
		Underlying percentage of patients with events			
		0.5%	1.0%	1.5%	2.0%
100	at least 1	0.394	0.634	0.779	0.867
	at least 3	0.014	0.079	0.190	0.323
200	at least 1	0.633	0.866	0.951	0.982
	at least 3	0.080	0.323	0.579	0.765

## 9.6 Data management

Patient-reported data on bleeds and infusions will be documented in a patient diary. Physicians document the study-relevant data for each patient in the eCRF. The CRF is available upon request (see Table 6).

A CRO will be selected and assigned for EDC system development. The eCRF will be part of the EDC system which allows documentation of all outcome variables and covariates by all participating sites in a standardized way. Information on the EDC system is available upon request (see Table 6). Detailed information on data management, including procedures for data collection, retrieval and preparation are given in the Data Management Plan (DMP), which is available upon request (see Table 6).

For information on quality control, refer to Section 9.8.

## 9.7 Data analysis

### 9.7.1 Statistical considerations

Statistical analyses will be of an explorative and descriptive nature. The study is not aimed to confirm or reject predefined hypotheses, hence no formal hypothesis testing will be performed.

Statistical analysis of the HEM-POWR sub-study will be mostly of exploratory nature, descriptive statistics can also be applied, and will be in the statistical section of the sub-study protocol.

All variables will be analyzed descriptively with appropriate statistical methods: categorical variables by frequency tables (absolute and relative frequencies) and continuous variables by sample statistics (i.e., mean, standard deviation [SD], minimum, median, quartiles, and maximum). Continuous variables will be described by absolute value and as change from baseline per analysis time point, if applicable.

All analyses will be performed for the total study population (overall analysis). Separate analyses for individual participating countries or regions will be provided if required for local reasons when sufficient data is available.

Sample size and disposition information including reasons for discontinuation by analysis time point will be displayed in a frequency table.

All therapies documented in the following forms will be coded using the World Health Organization Drug Global.

- Prior and concomitant medication
- Prior FVII treatment

Any diagnoses/diseases/event terms documented in the following forms will be coded using the latest Medical Dictionary for Regulatory Activities (MedDRA) version:

- General medical/surgical history
- Surgeries
- Adverse events

Annual analyses are planned to provide annual safety reports and preliminary results to support publications. The final analysis will be performed after end of the study, which is the date the analytical dataset is completely available.

All statistical details including calculated variables and proposed format and content of tables will be detailed in the Statistical Analysis Plan (SAP). Bayer AG will provide oversight of data analysis activities that will be assigned to a CRO. All specific processes and technical details will be documented by the CRO statistician in the SAP and tables specification manual. The SAP will be finalized before the first database lock. The SAP is available upon request (see [Table 6](#)).

### **Analysis populations:**

Patients who took at least 1 dose of damoctocog alfa pegol in the study will be eligible for safety analysis. The full analysis set (FAS) will include all SAF patients who have data on infusions and or bleeding events available. This will include patients who were not followed-up for 3 complete years of prophylaxis. PK analyses will be performed on the PK analysis set. The PK analysis set includes all SAF patients who have evaluable PK data.

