Data analysis	
Statistical analyses will be of an explorative and descriptive nature. The study is not aimed to confirm or reject predefined hypotheses; hence no formal hypothesis testing will be performed.
 
All variables will be analyzed descriptively with appropriate statistical methods: categorical variables by frequency tables (absolute and relative frequencies) and continuous variables by sample statistics (i.e., mean, standard deviation, minimum, median, quartiles, and maximum). Continuous variables will be described by absolute value and as change from baseline per analysis time point, if applicable.
 
It is planned to have an annual interim analysis of baseline characteristics starting 1 year after the First Patient First Visit, and further annual analyses are planned on prospective treatment outcomes.
 
For the primary analysis summary statistics of the number of total reported bleeds will be presented. ABRs will be calculated as the number of bleeding events divided by the length (in years) of the treatment regimen. ABRs will be characterized using descriptive statistics by calculating mean (<math>\pm</math> standard deviation), median, minimum, and maximum.
								
Milestones	
 
 First patient first visit:	Q2 2019	
 
 Last patient first visit:	Q2 2022	
 
 Last patient last visit:	Q2 2025	
 
 Final report:	Q1 2026	
 
	First patient first visit:	Q2 2019	Last patient first visit:	Q2 2022	Last patient last visit:	Q2 2025	Final report:	Q1 2026
First patient first visit:	Q2 2019								
Last patient first visit:	Q2 2022								
Last patient last visit:	Q2 2025								
Final report:	Q1 2026								

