## 7. Rationale and background

### 7.1 Epidemiology, classification, and treatment of hemophilia A

Hemophilia A is an X-linked, inherited, genetic bleeding disorder characterized by deficiency of clotting factor VIII (FVIII) [1],[2]. Hemophilia A comprises approximately 80% of all hemophilia cases, with an annual incidence of approximately 1 in 5,000 live male inhabitants [1],[2]. All races and economic groups are affected equally [1]. Prevalence estimates vary by country, ranging between 5 and 21 cases per 100,000 male inhabitants. According to the World Federation of

Hemophilia, it is estimated that only between 25% and 30% of hemophilia patients globally are adequately diagnosed and managed [3]. Furthermore, up to 75% of hemophilia patients globally live in developing countries in which access to specialist health care professionals and modern therapies prove to be a substantial barrier.

Normal FVIII levels vary between 50% and 150%. The severity of hemophilia A is classified by the amount of clotting factor present in the blood: mild, if the patient has >5% normal clotting factor (>0.05 international units [IU]/mL); moderate, if the patient has between 1% and 5% (>0.01 to 0.05 IU/mL) normal clotting factor; and severe, if the patient has <1% ( $\leq$ 0.01 IU/mL) normal clotting factor. Patients with mild or moderate hemophilia A typically have bleeds only following trauma, and tend to report fewer major health-related quality of life impacts. It is estimated that between 60% and 70% of patients with hemophilia A have the severe form of the disease [4]. For these patients, bleeding events often spontaneously occur in joints or muscles or with minimal or unknown trauma to the affected area [5]. Recurrent bleeding in the joints can lead to progressive joint damage, loss of joint mobility, and chronic pain.

The 2 main approaches to treatment are on-demand therapy, in which the patient is treated in response to a bleed, or prophylactically, in which the patient is treated regularly to prevent bleeding episodes. Prophylaxis is now considered standard of care in many countries, especially in the pediatric and adolescent population, as it has been shown to reduce complications from repeated bleeds, particularly joint arthropathy [2].

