### 9.2.2 Eligibility criteria

#### 9.2.2.1 Inclusion criteria

- Diagnosis of hemophilia A.
- Patients previously treated for Hemophilia A.
- Patients without previous history of inhibitors or patients with previous history of inhibitors on standard prophylaxis therapy for at least 1 year prior to study entry.
- No current evidence\* of FVIII inhibitor or clinical suspicion\*\* of FVIII inhibitor.
  - \* Evidence of FVIII inhibitor as measured by the Nijmegen-modified Bethesda assay [ $<0.6$  Bethesda units (BU/mL)] or Bethesda assay [ $<1.0$  BU/mL] in 2 on consecutive samples.
  - \*\* Documented or clinical suspicion of shortened FVIII half-life ( $<6$  hours).
- Initiation of or currently on damoctocog alfa pegol with any kind of treatment modality (on-demand, prophylaxis, or intermittent prophylaxis).
- Signed informed consent/assent.

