### **9.2.7 Visits**

The physician documents a first visit that corresponds to the initiation of the observational period (initial visit/baseline) in the eCRF/EDC system. Follow-up visits occur during routine practice, the study protocol does not define exact referral dates for those visits. After the initial visit, data collection will continue for 36 months (with the potential to be extended). Data collection occurs continuously throughout the observational period, i.e. each visit or assessment is to be documented in the eCRF/EDC system. Typical information to be collected are summarized in [Table 3](#).

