### **9.7.3 Analysis of treatment exposure**

Analysis of treatment exposure will be performed on the SAF.

In this study, the following 4 types of exposure based on physician's prescription will be considered:

- Prophylaxis: twice weekly (including any prescription more than 7 times per month).
- Prophylaxis: every 5 days (including any prescription between >5-7 times per month).
- Other: if not listed above.
- All.

The damoctocog alfa pegol exposure will start with the first infusion in the study. The period of continuous exposure per treatment pattern (following approved local label), stops whenever prescribed damoctocog alfa pegol treatment regimen changes. Treatment patterns for non-naïve patients will also be summarized.

Exposure duration (in days) will be analyzed descriptively by summary statistics and frequency tables per treatment pattern.

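### The full analysis set requires an in-study dose, so on-demand patients who never need an infusion drop out, which inflates the comparator ABR in the additional prophylaxis comparison and empties the on-demand bleed-free proportion

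*Protocol*

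**What the plan says.** Section 9.2.2.1 admits patients on any modality, on-demand included: "Initiation of or currently on damoctocog alfa pegol with any kind of treatment modality". Section 7.1 describes "on-demand therapy, in which the patient is treated in response to a bleed".

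Section 9.7.1 defines the sets in two steps. For safety: "Patients who took at least 1 dose of damoctocog alfa pegol in the study will be eligible for safety analysis". For effectiveness: "The full analysis set (FAS) will include all SAF patients who have data on infusions and or bleeding events available". The PK set is also drawn from the safety set, so every set that the protocol defines requires a dose taken in the study. No exception is written for on-demand patients.

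Section 9.7.4 puts the primary outcome, ABR, on the FAS and confines the primary ABR analysis to prophylaxis patients, with the observed prophylactic period as offset. When enough data have accrued, it adds an analysis "comparing the ABR in patients receiving prophylactic treatment with those who are not treated with standard prophylaxis". It also reports the proportion of bleed-free patients with a 95% CI.

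Two statements bear on time at risk. Section 9.7.3, on treatment exposure: "The damoctocog alfa pegol exposure will start with the first infusion in the study". Section 4 (Abstract): "ABRs will be calculated as the number of bleeding events divided by the length (in years) of the treatment regimen".

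**The concern.** A prophylaxis patient is infused on schedule whether or not he bleeds, so one dose in the study is close to automatic and says nothing about outcome. For an on-demand patient the first dose normally follows a bleed, so the same rule selects on the outcome. Dosing before enrolment does not help, because the dose must fall within the study. Section 11.2 itself allows for enrolled patients who have not yet received the product within the study.

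Two results are at stake: the additional ABR comparison, which would favour prophylaxis for a reason unrelated to treatment, and any bleed-free proportion reported for on-demand patients. The regression adjustment planned in Section 9.7.1 cannot recover patients who are outside the set. Low bleeders are lost most often. The protocol enrols mild patients on purpose (Section 9.2.6) and says in Section 7.1 that mild and moderate patients typically bleed only after trauma.

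**Working it through.** **Plan's own figure.** The protocol states no figure on this point. The stated figure that leans on the safety set is in Table 5: at least 3 patients with an event at 2.0% among 200, probability 0.765. The binomial tail gives 0.765. The fix leaves it alone, because the one-dose rule stays for safety.

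**Inputs.**
- Follow-up T = 3 years (Section 9.1), and T = 1 year as an illustration for the yearly interim analyses.
- Dispersion θ = 1 (Section 9.5). The protocol gives this for prophylaxis; using it for on-demand patients is an assumption.
- True on-demand ABR μ: not in the protocol. Assumed range 1 to 24 per year.
- Assumed: every bleed is infused, nothing else is infused, and follow-up is equal.

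**Formulas.** With a negative binomial count of mean μT and θ = 1:
- Share with no bleed, hence excluded: P0 = 1/(1 + μT).
- Mean count among those kept: μT/(1 − P0) = μT + 1.
- ABR among those kept, full follow-up counted: (μT + 1)/T = μ + 1/T.

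The excess is 1/T per year: 0.33 over 36 months and 1 over one year.

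| True ABR | Excluded, T = 3 | ABR shown, T = 3 | Excess | ABR shown, T = 1 |
|---|---|---|---|---|
| 1 | 1/4 = 25% | 1.33 | 33% | 2 |
| 2 | 1/7 = 14% | 2.33 | 17% | 3 |
| 6 | 1/19 = 5.3% | 6.33 | 5.6% | 7 |
| 12 | 1/37 = 2.7% | 12.33 | 2.8% | 13 |
| 24 | 1/73 = 1.4% | 24.33 | 1.4% | 25 |

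A simulation of 200,000 patients per row gave factors of 1.335, 1.169, 1.053, 1.030 and 1.014 at T = 3, in agreement within simulation error.

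**Effect on the comparison.** The prophylaxis-to-comparator rate ratio is multiplied by μ/(μ + 1/T). Over 36 months that is 1/1.33 = 0.75 at ABR 1, 2/2.33 = 0.86 at ABR 2 and 6/6.33 = 0.95 at ABR 6.

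**Bleed-free proportion.** Under the same assumptions the true value is P0 (25%, 14%, 5.3%, 2.7%, 1.4%). The value in the FAS is 0% in every row, since each patient kept has bled.

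**Conditional case.** If ABR time for on-demand patients also began at the first infusion, the simulated factor over 36 months would be 1.48 at ABR 2 and 1.19 at ABR 6 with the triggering bleed counted, or 1.27 and 1.13 without it. The protocol does not state that the ABR clock works this way.

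**The case against.** The strongest reply is about scope. The primary ABR is estimated in prophylaxis patients only and is not biased by this rule. The affected comparison is additional, depends on enough data, and sits in a study without formal hypothesis testing. All of that stands.

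The bias is also diluted. Patients not on standard prophylaxis can include those on intermittent prophylaxis, who infuse without a bleed. An on-demand patient can enter through an infusion for surgery or another event. A patient who switches from prophylaxis to on-demand is already dosed, and the assignment of switchers is left to the SAP. Section 9.5 expects the safety set to be close to enrolment, so few undosed patients are foreseen. These points reduce the size of the bias but do not remove it.

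A reader might infer more: that on-demand follow-up is counted only from the first treated bleed, so that bleed-free time is lost as well as bleed-free patients. The text does not establish this. The first-infusion rule stands in Section 9.7.3, which governs exposure analysis on the safety set and classes exposure by the physician's prescription. The Abstract divides bleeds by the length of the regimen, which can run before any infusion. Section 9.7.4 gives an explicit offset for prophylaxis only, and further detail may properly sit in the SAP. The larger factors under the conditional case are therefore not findings.

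The exclusion of undosed patients is not open in the same way, because the protocol itself fixes the FAS as a subset of the dosed patients.

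**Conclusion.** The point holds in a limited form. As written, the FAS drops on-demand patients with no infusion in the study and keeps bleed-free prophylaxis patients. That pushes the comparator ABR up and the on-demand bleed-free proportion down. The primary prophylaxis ABR is sound on this count.

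The size depends on an on-demand ABR that the protocol does not give, on θ = 1 borrowed from prophylaxis, and on infusion for bleeds only. Over 36 months the inflation is 33% at a true ABR of 1, 17% at 2 and under 3% at 12 or more. Early interim analyses would be worse, since one year of follow-up adds a full bleed per patient. The direction is clear; the magnitude matters mainly for low bleeders and short follow-up. For the bleed-free proportion the distortion is complete wherever bleeds are the only reason to infuse.

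This should be corrected because the repair is cheap. It is not a threat to the main result.

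**What to change.** Define the effectiveness set in Section 9.7.1 as all enrolled patients prescribed damoctocog alfa pegol with at least one follow-up at which bleeds were recorded or asked about, whether or not a dose was taken. Keep the one-dose rule for the safety set. The bleed data should already exist, since Table 3 (footnote 4) has the physician ask about bleeds at each visit.

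State in Section 9.7.4 that ABR time for on-demand periods runs from the later of the initial visit and the start of the prescribed on-demand regimen, not from the first infusion. Leave the prophylaxis offset as written: moving every group to the initial visit would add pre-dose time for new prophylaxis starters, because Section 9.2.7 places baseline before the first administration.

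The cost is wording. The FAS is no longer nested in the safety set and gains a few undosed on-demand patients, so disposition tables must show the two sets separately. Treatment and data collection do not change.
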